- Incident or prevalent cases of SMI: including schizophrenia, schizoaffective disorder, bipolar disorder, major depressive disorder, and psychosis NOS with some evidence of functional impairment.
- Age 18 years and older.
- Recent treatment with a 2GA, e.g., having received treatment with a standing 2GA anytime in the past 6 months. Concomitant psychotropic medications will be allowed as there are no contraindications with this regimen. Ongoing treatment of their mental illnesses at one of three mental health clinics: McLean Hospital (McLean outpatient clinicians), BayCove, Edinburg Center, and Mass Mental Health Center, defined as entering one of the treatment programs as a de novo patient (new disease) or having been diagnosed >2 years ago and had at least six visits in the past 12 months (prevalent disease).

The exclusion criteria are as follows:

Unstable/active disease or potential contraindications, e.g., diabetes, unstable
angina or recent acute coronary syndrome, pregnancy, very high risk factors on
the screening labs (e.g., CPK>2*ULN, liver disease (AST> 2*ULN ALT> 2*ULN)

; A1c>7%;), renal failure (creatinine ≥1.3mg/dL or GFR<60 mL/min/1.73m²), liver failure, or both statin and angiotension drug contraindications (when possible we will provide the study medication that does not interact with previously prescribed medications, i.e. subjects taking lithium will only be prescribed simvastatin since anti-hypertensives are contraindicated with lithium). Participants whose screening labs indicate high cholesterol (LDL > 200 mg/dL), hypertension (SPB > 160 mmHg), or hypotension (SBP< 120 mmHg) will be included; however we will not prescribe both study medications; we will only provide the study medication that can be taken safely. For example, a participant with high cholesterol will be referred to their PCP for care and administration of a statin, but could still receive losartan in the treatment arm.

- Unable to provide informed consent, e.g., has dementia, developmental disability, other cognitive disorder, or fails screening mini-mental status exam.
- Women who are pregnant or breastfeeding

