Analysis of Aim 3: Per-Protocol Effect on Cardiovascular Risk Factors: For Aim 3, we will study the same composite and individual risk factor outcomes as for Aim 2, but will estimate the per-protocol effect rather than the ITT effect. ITT is the effect of assignment to the strategies of interest; the per-protocol effect is the effect of following the strategies as indicated in the protocol and is the implicit target of inference. To estimate the per-protocol effect, however, one needs to make assumptions similar to those commonly made in the analysis of observational studies. Specifically, when adjusting for measured covariates, the valid estimation of the per-protocol effect requires that all fixed and time-varying factors that jointly predict the outcome and adherence to the assigned intervention are measured without error. We will adopt two analytic approaches, both involving adjustment via inverse probability (IP) weighting. Analysis approach 1: We will artificially censor participants when they stop adhering to the assigned strategy. We will censor subjects in the active treatment arm if/when their adherence drops below 80% of the intended dose, based on estimates of the proportion of days covered (PDC). [141-144] In sensitivity analyses, other adherence cutoff points will be used, as in our other past studies.^[145] For subjects in the control arm, we will follow two censoring strategies: (i) subjects will be censored if/when they start taking one of the drugs assigned to the active treatment arm, (ii) subjects will never be censored, which is equivalent to interpreting any treatment they receive as standard of care. We will conduct separate analyses under each of these two censoring strategies. We will compare the average outcome between arms at pre-specified time points during the follow-up. The outcome models will be similar to those described for Aim 2, but they will be fit to those remaining uncensored at the corresponding time. This approach requires no assumptions about the dose-response curve for adherence because only adherent subjects contribute to the fit of the outcome model.

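### Aim 3, approach 1, control strategy (i): for participants eligible for only one study drug, a control is censored for starting a drug class that an intervention participant may start and stay in

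*Protocol*

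**What the plan says.** Protocol section VI, Analysis of Aim 3, sets the target: "the per-protocol effect is the effect of following the strategies as indicated in the protocol". Approach 1 pursues it by artificial censoring with inverse-probability weights, using different rules by arm.

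- Intervention arm: "We will censor subjects in the active treatment arm if/when their adherence drops below 80% of the intended dose", measured by proportion of days covered. Starting a drug prescribed elsewhere is not a trigger.
- Control arm, strategy (i): "subjects will be censored if/when they start taking one of the drugs assigned to the active treatment arm". No exception is stated.
- Control arm, strategy (ii): "subjects will never be censored, which is equivalent to interpreting any treatment they receive as standard of care".

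Both control strategies will be run: "We will conduct separate analyses under each of these two censoring strategies". Neither is named as primary. Approach 2 uses no artificial censoring.

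The exclusion criteria in Protocol section III keep people with screening LDL above 200 mg/dL in the trial but withhold one study drug from them. The example given is that "a participant with high cholesterol will be referred to their PCP for care and administration of a statin, but could still receive losartan"; the losartan part concerns those randomised to the intervention. Screening laboratory results come before random assignment (Table 1, Steps 2 and 3), so the criterion for referral does not depend on arm.

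The SAP describes per-protocol analyses only as supplemental and appropriately adjusted. It does not restate or replace these censoring rules.

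**The concern.** A per-protocol contrast should count the same behaviour as deviation, or as permitted, in both arms unless the strategies themselves differ on it. Here the protocol points a participant with high LDL to a statin from primary care. Acting on that advice departs from neither strategy, yet strategy (i) treats it as a deviation in a control and as irrelevant in an intervention participant who is on losartan only.

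The result is that the intervention mean keeps LDL falls produced by primary-care statins, while the control mean is rebuilt from referred controls who did not start one. Part of the effect of a referral meant for both arms is then credited to the intervention, on LDL and on the composite risk score. A related case is a control already on a statin, for whom losartan is the only trial drug, who is switched to simvastatin or atorvastatin. The plan does not say whether such a switch counts as starting a drug.

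**Working it through.** **Step 1: apply each rule to the same person.** Take a participant with LDL above 200 mg/dL who starts a primary-care statin that is also an active-arm drug.

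| Analysis | Intervention, losartan only | Control |
|---|---|---|
| Approach 1, strategy (i) | kept while losartan adherence is at least 80% | censored |
| Approach 1, strategy (ii) | kept while losartan adherence is at least 80% | kept |
| Approach 2 | no artificial censoring | no artificial censoring |
| Aim 2 ITT | kept | kept |

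The general censoring list in Protocol section IV, Follow-up (diabetes, cardiovascular or cerebrovascular event, death, leaving the care system), does not include a statin start, so it does not close the gap in the first row.

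**Step 2: size.** The protocol gives no figure to reproduce. Let f be the share referred, u the uptake of the primary-care statin (taken as equal in both arms) and D the LDL fall on it. Among referred participants the retained intervention mean is shifted by -uD. The control mean, weighted up from those who did not start, is shifted by 0. The contribution to the overall contrast is f × u × D in favour of the intervention. If referred starters were kept in both arms, or censored in both, it would be zero.

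Assumed ranges: f 2%, 5% or 10%; u 40-65%; D 50-75 mg/dL; SD 35 mg/dL. With the 150 per arm in the Power Calculations, SE = 35 × √(2/150) = 4.04 mg/dL.

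| f | Low end | High end | In SE |
|---|---|---|---|
| 2% | 0.02 × 0.40 × 50 = 0.4 | 0.02 × 0.65 × 75 = 1.0 | 0.1-0.2 |
| 5% | 0.05 × 0.40 × 50 = 1.0 | 0.05 × 0.65 × 75 = 2.4 | 0.25-0.6 |
| 10% | 0.10 × 0.40 × 50 = 2.0 | 0.10 × 0.65 × 75 = 4.9 | 0.5-1.2 |

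These are upper figures. They count every statin start, whereas on the narrowest reading only the named statins (simvastatin, atorvastatin) trigger censoring. Artificial censoring also makes the real SE larger than 4.04, so the ratios would be smaller.

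**Step 3: does weighting cure it?** A simulation of 2,000,000 participants used weights by referral stratum. It assumed f = 5%, u = 60%, D = 80 mg/dL, a study-statin effect of 40 mg/dL and 15% initiation among non-referred controls. The contrast without carry-over was -38.0 mg/dL. Strategy (i) as written gave -40.4. The gap of 2.4 equals 0.05 × 0.60 × 80. Keeping referred starters in both arms, or censoring them in both, returned -38.0. Weighting corrects for who is censored, not for which treatments each arm's rule allows. If nearly all referred controls start the statin, few remain to be weighted up.

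**Step 4: strategy (ii).** In the same simulation it gave -32.3. Its distance from -38.0 is the treatment started by non-referred controls, 0.15 × 40 × 0.95 = 5.7. The referral part cancels.

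**The case against.** Several points on the other side have force.

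- A reader might infer that Aim 3 as a whole is biased. The documents do not support that: strategy (ii) stands in the same sentence as strategy (i), and approach 2 does not censor. Neither, however, replaces strategy (i). Strategy (ii) counts all control treatment as usual care, which is a different contrast, and approach 2 states no rule for drug starts in controls. The protocol commits to reporting strategy (i).
- The trigger is undefined. It could mean the four named drugs, their classes, or the drug that the individual would have been assigned. On the last reading a control with LDL above 200 mg/dL is not censored for a statin, and the problem disappears. The text speaks of drugs assigned to the arm, so the literal reading is broader, but the intended meaning cannot be settled from the documents.
- A reader might take it as settled that controls are referred at the same rate. The exclusion criteria imply referral regardless of arm, and Follow-up provides for recommendations in either arm. But the Control paragraph says that staff will not try to influence control treatment and will not intervene outside emergencies, and section V says that routine laboratory results are not passed to the primary care physician. These passages must be reconciled. The bias from the censoring rule scales with uptake among controls. The Power Calculations expect fewer than 15% of all controls to start treatment; at 15%, f = 5% and D = 75, it is 0.05 × 0.15 × 75 = 0.6 mg/dL.
- A reader might extend the point to blood pressure. The protocol states a primary-care referral only for high cholesterol, so no such bias is claimed.

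**Conclusion.** The point holds for Aim 3, approach 1, control strategy (i), read literally. The arms are treated asymmetrically for participants eligible for one study drug. To the extent that referral and uptake occur in both arms, the LDL and composite-risk contrast shifts toward the intervention, and weighting does not remove the shift.

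Its size is at most about 0.4-4.9 mg/dL, or 0.1-1.2 SE, and rests wholly on assumed values: the documents give no share above 200 mg/dL, no uptake, no LDL fall and no SD. Only the assumed 10% share brings it to 1 SE. The within-class switch case is not sized and would add only the incremental effect of a switch.

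The SAP's primary outcome and the Aim 2 ITT analysis are unaffected. The rule is worth correcting because its error has a known direction, not because it threatens the trial's main result.

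**What to change.** Add one sentence to strategy (i): a control is censored only on starting a drug class that they would have been prescribed had they been assigned to the intervention, given baseline eligibility (statin only, ARB only, or both). State also that starts in a class the protocol withheld from that person, and switches within a class already in use, do not censor in either arm.

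The SAP's primary outcome definition already separates participants eligible for both drugs from those eligible for one, so no new data are needed. Section VI (Analysis of Aim 2) promises to finalise the analytic protocol before outcome data are examined, and the sentence can go in then. It would help to say at the same time which control strategy is primary for Aim 3.

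The cost is small: the control strategy becomes participant-specific and needs a line of explanation in the report. No referral or clinical rule changes. Separately, the sponsor should reconcile the referral text with the statements on leaving control treatment alone.

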Outpatient Bipolar Clinic. After running data queries using the study's inclusion and exclusion criteria, we will request detailed data through RPDR in order to directly contact those patients who are eligible for the study and who have consented to be contacted in future for research purposes. Detailed data requests, including identifying information such as medical information and contact information, will be approved by the Partners IRB.

Random (1:1) allocation: We will assess eligibility, NP's will conduct the informed consent process, then randomize eligible subjects to one of two arms: 1) fixed-dose statin and/or ARB; or 2) usual treatment with greater monitoring. In both arms, the patient's clinical care remains within the original mental health clinics. We will use a computerized random number generator. Participants unable to be randomized due to eligibility issues discovered at the first study visit will still be followed as not-randomized subjects.

Randomization scheme: We will start with a concealed, simple subject-level randomization scheme, e.g., web or telephone delivered random sequence. [104-106] We also will consider concealed, block randomization schemes, e.g., accounting for clinic and time with randomly varied block sizes. An investigator not involved in the arm assignment or clinical care of subjects will perform the generation and allocation concealment.

Intervention: The multi-component intervention exploits a number of strategies from incentive theory and behavioral economics, including: a) a simplified drug regimen; b) free treatments; c); framing of goals and goal setting; and d) focus on immediate cardiovascular risks within a larger plan for risk reduction.^[107-114]

Control: We will compare the initial treatment intervention with usual treatment (control arm), with both arms superimposed on a system of regular monitoring base. The RA/APRN pair will make no effort to alter or influence treatment or use of that treatment for subjects in the control arm. Note that our goal in the Control arm is to characterize "usual treatment". We will not intervene in this care except in emergencies requiring us to notify the patient's treatment team. Some patients who need care for metabolic syndrome may not be receiving it – just as they would if not in our trial.

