Characterization of Usual Treatment: We also will carefully describe care under Usual Treatment, including the timing of initiation, treatment choice, adherence, prescribing clinicians, and visit patterns for subjects in the control arm. We will characterize the involvement of other clinicians for subjects in both arms, and clinic traits.

Treatment Operational Definition: To start, we will use the same treatment definition for both study arms, i.e., current use of a statin and angiotensin drug. Because there are multiple potential drugs for cardiovascular prevention, we will alter this definition in a series of sensitivity analyses. For example, we will examine a minimal cardiovascular treatment variable in which we define treatment as current use of any cardiovascular drug, independent of the therapeutic class or mechanism of action. We also will examine a partial treatment variable in which we count the number of distinct cardiovascular prevention drugs.

Analysis approach 1: We will plot the percent on "adequate" CVD prevention care, at baseline and the four quarterly follow up times to monitor how treatment activity unfolds over time in the two arms of the trial. At any given follow-up point we will be comparing

two binary outcomes (on or off treatment) and will use standard methods for comparing two proportions to test statistical significance and get confidence intervals for the difference in the percent on treatment in the two arms. We will use a Bonferroni correction so the four separate tests or CIs will have an overall level of 0.05 or 95% CI, respectively.

Analysis approach 2: We will use all available follow-up data to construct a summary measure of the mean percentage of follow-up time during which each group was on treatment. Since we expect the distribution of outcomes to be non-normally distributed, we will get a test of significance for no difference between the mean outcomes in the two arms using a randomization test. A 95% confidence interval for the difference of percentage of time on Tx will be obtained using bootstrap methods. We will use STATA 13.0 for all analyses.

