Analysis approach 2: We will estimate the parameters of structural models that specify the dose-response curve for adherence in the treatment arm. We will use a flexible dose-response function that incorporates information on both cumulative dose and recency, and builds on previous trial data. This analytic approach is more statistically efficient because it does not involve artificial censoring, but will require extensive sensitivity analyses to ensure that the estimates are not sensitive to the choice of dose-response function.

Power Calculations: We anticipate having adequate power for this trial. To illustrate, we will focus on comparison of treatment use at one time point. By design, all subjects in the intervention arm will receive cardiovascular prevention treatment, while none in the control arm (usual treatment) will have started treatment. At each follow-up time point,

some intervention subjects could be non-adherent (no use), and some control subjects could have started treatment (use). We will test the significance of (with confidence intervals) the difference in the percent on treatment between the two study arms at each time point separately, using Bonferroni multiple comparison methods (exam-specific alpha=0.05/4 to get an overall test with alpha=0.05). Based on the literature, <15% of control subjects might initiate treatment. With one-sided alpha =0.0125 and 150 subjects in each comparison group (classifying subjects lost to follow-up as not on care so that sample size is constant), we estimate having 80% power to detect a 26% difference in use, and 90% power to detect a 20% in cardiovascular treatment use. We also have adequate power (90%) to detect clinically sensible cardiovascular risk changes (e.g., one standard deviation change in LDL levels in the absence of treatment), using modified two-sample normal theory and comparable assumptions (details available on request).

VII. Risks and Discomforts

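### Aim 1 is powered on a one-sided 0.0125 test per visit, but the sidedness of the tests is unstated and the promised overall 95% intervals, read as two-sided, need a stricter critical value

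*Protocol*

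**What the plan says.** Protocol section VI, Analysis of Aim 1, Analysis approach 1, plots the percentage on treatment "at baseline and the four quarterly follow up times". At any follow-up point the analysts "will use standard methods for comparing two proportions to test statistical significance and get confidence intervals for the difference". On multiplicity it adds: "We will use a Bonferroni correction so the four separate tests or CIs will have an overall level of 0.05 or 95% CI, respectively". No side is given for the tests or the intervals.

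The Power Calculations paragraph repeats the per-visit level, "exam-specific alpha=0.05/4 to get an overall test with alpha=0.05", again without a side. The sample-size statement then reads: "With one-sided alpha =0.0125 and 150 subjects in each comparison group". This is the only place in either document where a side is named. The control-arm assumption is: "Based on the literature, <15% of control subjects might initiate treatment". The stated results are 80% power for a 26-point difference and 90% power for a 20-point difference.

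The SAP (Analysis of the primary study outcome) has one difference in means, one 95% interval and one p-value. It has no visit-by-visit tests, no Bonferroni rule and no stated side.

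**The concern.** The same number, 0.0125, serves as the Bonferroni share for tests and intervals and as a one-sided level for power. These are the same rule only if the intervals are one-sided too. With ordinary two-sided intervals, the test that was powered is easier to pass than the interval is to clear of zero. A visit could then be reported as significant beside an interval that includes no difference, and the plan does not say which result governs.

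If the tests are meant to be two-sided, the inconsistency lies in the power sentence, which then uses too small a critical value. Either way, a choice that should be fixed before outcome data are seen is left open.

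**Working it through.** **Inputs.** Four visits and a per-visit level of 0.05/4 = 0.0125 (Analysis approach 1 and Power Calculations); "150 subjects in each comparison group" with 1:1 allocation; control use 15%, the upper end of the stated range, with 10% and 5% as sensitivity values.

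**Critical values.**
- One-sided 0.0125: z = 2.241. This is also the critical value of a two-sided 97.5% interval, and four of those have guaranteed simultaneous coverage of 1 − 4 × 0.025 = 90% (a Bonferroni lower bound).
- Two-sided 0.0125: z = 2.498, matching a two-sided 98.75% interval. Four of those guarantee 1 − 4 × 0.0125 = 95%.

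**The plan's own power figures.** For a pooled-variance test of two proportions, with d = p2 − p1 and p̄ the mean of the two:

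power = Φ{[d√n − z√(2p̄(1 − p̄))] / √[p1(1 − p1) + p2(1 − p2)]}

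15% vs 35%, n = 150: d√n = 0.20 × 12.247 = 2.449; √(2 × 0.25 × 0.75) = 0.612; denominator √(0.1275 + 0.2275) = 0.596.
- z = 2.241: (2.449 − 1.373)/0.596 = 1.807, power 96.5%.
- z = 2.498: (2.449 − 1.530)/0.596 = 1.544, power 93.9%.

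15% vs 41%, n = 150: d√n = 3.184; √(2 × 0.28 × 0.72) = 0.635; denominator √(0.1275 + 0.2419) = 0.608.
- z = 2.241: (3.184 − 1.423)/0.608 = 2.898, power 99.8%.
- z = 2.498: (3.184 − 1.586)/0.608 = 2.630, power 99.6%.

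| Quantity (control 15%, 150 per arm) | Stated | One-sided 0.0125 | Two-sided 0.0125 |
|---|---|---|---|
| Power, 20 points | 90% | 96.5% | 93.9% |
| Power, 26 points | 80% | 99.8% | 99.6% |
| Detectable difference, 80% power | 26 points | 14.8 points | 16.2 points |
| Detectable difference, 90% power | 20 points | 17.1 points | 18.6 points |
| n per arm for 90% power, 20 points | – | 115 | 132 |

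Neither stated figure reproduces. They also run backwards: at a fixed sample size, level and control rate, the larger difference cannot have the lower power. Control rates of about 30% to 50% bring one-sided power at 20 points to 89.4–90.7%, but that contradicts the assumption of under 15%. Power at 26 points with 150 per arm was at least 98% at every control rate tried, one- or two-sided. Lower control rates raise power: two-sided power at 20 points is 97.1% with 10% control use and 99.3% with 5%.

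**A result on which test and interval disagree.** Take 22/150 (14.7%) vs 38/150 (25.3%), a difference of 10.7 points.
- Test: pooled proportion 0.20, standard error √(0.2 × 0.8 × 2/150) = 0.0462, z = 0.1067/0.0462 = 2.309, one-sided p = 0.0105, below 0.0125.
- Two-sided 98.75% Wald interval: unpooled standard error 0.0458; 10.7 ± 2.498 × 4.58 gives −0.8 to 22.1 points, which includes zero.

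With 22 vs 39 the same happens (z = 2.439, p = 0.0074, interval −0.2 to 22.8). With 22 vs 40 the two agree.

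**How often.** The chance that z falls between the two critical values at a visit is 0.6% under no difference. With 15% control use it is about 10% for a true difference of 10 to 12 points, 2.6% for 20 points and 0.2% for 26 points.

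**The case against.** The strongest reply is that no contradiction is written down. The word one-sided belongs to a power illustration; the sentences that define the tests and intervals name no side. Two-sided tests at 0.0125 agree with 98.75% intervals, apart from small differences between pooled and unpooled variances. One-sided tests agree with one-sided 98.75% bounds, and four of those also give at least 95% overall. The conflict needs one-sided tests together with two-sided intervals. This stands, and it makes the disagreement conditional. It does not settle which rule applies, and under the usual two-sided reading of an interval for a difference, either the tests or the power sentence is out of line.

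A reader might infer three stronger things that the documents do not support.
- That the false-positive rate is doubled. Four one-sided tests at 0.0125 sum to at most 0.05, which is the overall level the protocol declares. The 2.5% in the favourable direction follows only from a two-sided convention that the protocol does not state.
- That the stated power belongs to the looser rule and would fall if corrected. The looser rule gives 96.5% and 99.8%, not 90% and 80%, and the two-sided figures also exceed those stated.
- That the trial's primary result is at risk. The SAP's primary analysis is one comparison without visit tests.

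**Conclusion.** The point holds as a minor inconsistency. Sidedness is unstated for the Aim 1 visit tests and intervals, and the one-sided power basis does not match conventional two-sided intervals with overall 95% coverage. The gap is 2.241 against 2.498 in critical value, 2.6 percentage points of power at a 20-point difference (96.5% less 93.9%, before rounding), and about 1.5 points in the difference detectable with 90% power. It does not affect the sample size: 132 per arm suffices for 90% power at 20 points under the stricter rule, and 150 are planned.

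The power figures in the same paragraph need replacing whichever side is chosen, because they run backwards and do not follow from their own inputs.

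These conclusions rest on 15% control use, normal-approximation tests of two proportions and two-sided intervals; the last is a convention, not something the protocol says.

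**What to change.** In Analysis approach 1, state that each of the four follow-up tests is two-sided at 0.0125 and is reported with a two-sided 98.75% interval. In Power Calculations, remove the one-sided level and restate the result: with 15% control use and 150 per arm, power is 93.9% for a 20-point difference and 99.6% for 26 points, and the detectable difference is about 16.2 points at 80% power and 18.6 points at 90%.

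A one-sided rule used throughout, with one-sided 98.75% bounds, would also be coherent, but it would have to be stated. The two-sided version is preferable because it is how such intervals are normally read.

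The cost is two wording changes. No extra participants or design changes are needed, and the corrected power at both differences is higher than what the protocol now states.

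### The power statement gives 80% power for a 26-point difference and 90% for a smaller 20-point difference at the same sample size and alpha; both cannot hold, and 26 points at 80% follows from no control rate

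*Protocol*

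**What the plan says.** The Power Calculations paragraph in Protocol section VI illustrates power with the percent on treatment at one follow-up visit, compared between the two arms. Its inputs are:

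- **Sample size and alpha:** "With one-sided alpha =0.0125 and 150 subjects in each comparison group". The alpha is a Bonferroni share over four visits: "exam-specific alpha=0.05/4 to get an overall test with alpha=0.05".
- **Control use:** "Based on the literature, <15% of control subjects might initiate treatment".
- **Loss to follow-up:** handled by "classifying subjects lost to follow-up as not on care so that sample size is constant". No loss rate is given.

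The result is: "we estimate having 80% power to detect a 26% difference in use, and 90% power to detect a 20% in cardiovascular treatment use". A word is missing after the second percentage; I read it as a difference, like the first.

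The paragraph then adds a separate claim for risk factors, "We also have adequate power (90%) to detect clinically sensible cardiovascular risk changes", and offers the details only on request. The SAP contains no power calculation.

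**The concern.** One sample size, one alpha and one control-rate assumption serve two pairs of figures that run the wrong way: the larger difference is given the lower power. At least one pair must be wrong.

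What is at stake is the meaning of the sample size. The risk-factor claim cannot be checked, so the treatment-use comparison is the only one whose stated inputs allow the reader to test 150 per group. If that statement is wrong, the reader does not know what difference the trial can detect, and a small or null difference at a visit would be judged against the wrong yardstick.

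**Working it through.** **Inputs.** From the Power Calculations paragraph: n = 150 per group; one-sided alpha = 0.05/4 = 0.0125, so z = 2.2414; control rate p0 at most 0.15; lost subjects counted as off treatment, so n stays at 150. The test is a standard comparison of two proportions (Aim 1, Analysis approach 1).

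**Formula.** With p1 = p0 + d and p̄ = (p0 + p1)/2:

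- SE0 = √[2 p̄(1 − p̄)/n]
- SE1 = √[p0(1 − p0)/n + p1(1 − p1)/n]
- power = Φ[(d − 2.2414 × SE0)/SE1]

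**1. The plan's own figures at 15% control use.**

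- 20 points (15% vs 35%): SE0 = 0.0500, SE1 = 0.0486; (0.20 − 0.1121)/0.0486 = 1.807; power 96.5%. Stated: 90%.
- 26 points (15% vs 41%): SE0 = 0.0518, SE1 = 0.0496; (0.26 − 0.1162)/0.0496 = 2.898; power 99.8%. Stated: 80%.

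One-sided Fisher exact tests give 95.7% and 99.7%, so the choice of test does not explain the gap.

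**2. Other control rates.**

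| Control use | Power, 20 points | Power, 26 points | Detectable at 80% / 90% power |
|---|---|---|---|
| 5% | 99.7% | 99.99% | 10.8 / 12.8 points |
| 10% | 98.5% | 99.95% | 13.2 / 15.4 points |
| 15% | 96.5% | 99.8% | 14.8 / 17.1 points |

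Over all possible control rates, the lowest 26-point power is 99.0%, at 37% vs 63%. With 0.00625 in each tail it is 98.1%. The lowest 20-point power is 89.4%, at 40% vs 60%, so exchanging the two differences does not work either: 20 points never falls to 80%.

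**3. Sample size implied by 26 points at 80% power.** This needs 56 per group at 15% control use and at most 69 at any control rate, against 150 planned.

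**4. Could an unstated loss rate explain it?** Suppose the rates describe retained subjects and a fraction L is lost and counted as off treatment. Equal loss multiplies both rates by (1 − L), with n still 150. This model is my assumption. At 15% control use:

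- 20 points reaches 90% power at L = 18.8% in both arms (12.2% vs 28.4%). The same loss gives 98.6% at 26 points.
- 26 points reaches 80% power only at L = 54.6% in both arms (6.8% vs 18.6%). The same loss gives 59.5% at 20 points.
- With loss in the intervention arm only, 90% at 20 points needs 8.2% loss (26-point power 98.9%), and 80% at 26 points needs 27.4% loss (20-point power 50.2%).

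No single loss rate gives both figures.

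**5. Detectable differences with loss or two-sided testing** (15% control use, 80% / 90% power):

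| Equal loss | One-sided 0.0125 | 0.00625 per tail |
|---|---|---|
| None | 14.8 / 17.1 | 16.2 / 18.6 |
| 10% | 16.0 / 18.5 | 17.5 / 20.1 |
| 20% | 17.4 / 20.2 | 19.1 / 22.0 |

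With loss, the differences are those among retained subjects.

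**The case against.** The strongest reply is that this matters little. The calculation is offered as an illustration, the error understates power, and the claim of adequate power survives for this comparison. It also concerns a one-visit comparison with a four-visit Bonferroni correction, whereas the SAP's primary outcome is each subject's proportion of the 12 months on medication, analysed by regression as a difference in means. Correcting the sentence therefore does not supply power for the SAP's primary analysis. All of this stands and limits the weight of the point, but it does not make the sentence right.

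The 20-point figure can also be defended without any loss assumption. Taken near maximum variance (40% vs 60%), power is 89.4%, so 90% could be a conservative value. That uses control rates well above the protocol's own limit of 15%, but it is a reasonable account of that half of the sentence.

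The missing word leaves room to read the 20% as a level of use. Against a control rate of about 6%, 20% use has roughly 90% power (91.8% for 20% vs 6%). This does not help the first figure, which is explicitly a difference. The 26 may be a slip for 16, since the two-sided difference at 80% power is 16.2 points, but the documents do not confirm it.

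**Conclusion.** The concern holds. On the stated inputs the two power figures contradict each other, and the 26-point figure at 80% power reproduces at no control rate unless a large, unstated loss is assumed, which then breaks the 20-point figure. The 20-point figure at 90% is defensible only as a conservative value or with an unstated loss of about 19% in both arms.

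Read as written, the detectable difference is 20 to 26 points; on the plan's own inputs at 15% control use it is about 15 to 17 points. This rests on the normal approximation with pooled null variance, one-sided alpha 0.0125, and rates taken after lost subjects are counted as off treatment. It is an error of statement that should be corrected. It does not show that 150 per group is too few.

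**What to change.** Replace the sentence with one that states every input. For example: with 150 per group, 15% use in controls and one-sided alpha 0.0125, power is 80% for a difference of about 15 points and 90% for about 17 points at a single visit, where the rates are those observed after subjects lost to follow-up are counted as off treatment.

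- If a loss rate was assumed, state it and give the matching difference among retained subjects: about 17 and 20 points at 20% loss in both arms.
- If the Bonferroni tests or intervals are meant to be two-sided, give about 16 and 19 points without a loss adjustment, or about 19 and 22 points with 20% loss in both arms.
- Say that the calculation covers the one-visit comparison, not the SAP's primary outcome.

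The cost is one or two sentences, with no extra patients and no change to the analysis.
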